Objectives	To quantify the benefit of integrating the new biomarker Copeptin into the process of managing patients with suspected non ST-elevation acute coronary syndrome (N-STEACS) with a negative baseline Troponin test result in the Emergency Department. Hypothesis : Patients with suspected ACS with a negative baseline Troponin who test negative for Copeptin at admission are at low risk of ACS and can safely be discharged into ambulant care. Secondary hypotheses: Patients with suspected ACS with a negative baseline Troponin who test positive for Copeptin at admission are at risk for ACS and should be evaluated as by standard of care. The Integration of Copeptin into the CPU process will shorten the patient's length of Emergency Department/ CPU and hospital stay and will improve patient satisfaction.
Study Design	Multicentre, open, randomized, controlled clinical trial (RCT) Interventional diagnostic biomarker trial 1:1 Randomization in two study arms with differing process management: a) interventional/experimental arm (Integration of Copeptin) b) control/ standard arm (Copeptin not available to treating staff)
Number of Sites	3 sites in Germany, 1 site in Switzerland and 1 site in Austria
Experimental Diagnostic Process	Experimental Arm: Patients with the above described characteristics who test negative for Copeptin at admission will be considered low-risk and will be discharged into ambulant care without further interventions. Patients with the above described characteristics who test positive for Copeptin at admission will be evaluated as by standard of care according to current guidelines..
Standard Diagnostic	Control Arm:

Process	Copeptin result will not be revealed to the treating physicians. Patients will be evaluated as by standard of care according to current guidelines.
Gold Standard	DGK / ESC / AHA Guidelines for the management of patients with suspected Non-ST-elevation ACS (NSTEMACS)
Time Schedule	Date of study / recruitment start: February 2011 Date of termination of recruitment: February 2012 Date of study termination: Autumn 2012
Total Number of Patients	n=446 per treatment group (total number of patients 892)
Study Population	Men and women of full age with suspected Non-ST-elevation acute coronary syndrome (NSTEMACS) and negative baseline Troponin.
Inclusion Criteria	Admission to the Emergency Department with symptoms consistent with ACS: - Typical chest pain (with or without ECG-changes, but no ST-elevation) suggestive of unstable angina or non-ST-elevated myocardial infarction (NSTEMI) - Troponin negative at admission according to the current clinical practice Patient willing and able to give written informed consent
Exclusion Criteria	Patients with ST-elevation myocardial infarction (STEMI) Continuing chest pain or recurrent episodes of chest pain under therapy High-risk patients with suspected ACS who need to be hospitalized for reasons independent of their initial troponin result Patients who need to be hospitalized for other medical reasons Patients in need of urgent life-saving interventions Patients under 18 years of age Patients with a life expectancy < 6 months Patients with any condition that leads the treating physician to not consider the patient eligible for the trial
Study endpoints	Primary Endpoint: Rate of MACE (all- cause death or survived sudden cardiac arrest, myocardial infarction, re-hospitalisation for acute coronary syndrome, acute unplanned PCI, coronary artery bypass grafting (CABG) and documented life-threatening arrhythmias (VF, VT, AV-block III)) within 30 days Copeptin vs. Control group Secondary endpoints: Efficacy endpoint of rate of Patients in whom coronary angiography is performed Rate of Patients requiring PCI due to their findings in cardiac catheterization. Rate of bleeding events at 30 and 90 days defined as non-CABG intracranial, intraocular, or retroperitoneal bleeding; access-site hemorrhage requiring intervention or resulting in a ≥ 5 cm diameter hematoma; reduction in hemoglobin concentration of ≥ 4 g/dL without or ≥ 3 g/dL with an overt bleeding source; reoperation for bleeding; or blood product transfusion. Further secondary endpoints evaluate efficacy, safety, cost effectiveness and patient satisfaction of the new process including length of stay in the hospital
Safety	All major cardiac adverse events (MACE) as defined in the protocol and bleeding complications as defined in the protocol will be assessed and documented for the duration of the study.
Withdrawal Criteria	
 • Patients who are eligible for discharge from their cardiac situation but cannot be discharged for other medical reasons will be excluded from the trial • Patients who withdraw their consent will be excluded from the trial • Patients who violate the protocol will be excluded from the trial

3 Study-Design

Studiendesign BIC-8: Copeptin as a rule-out marker in ACS

4 Introduction

4.1 Introduction and background

The term “acute coronary syndrome (ACS)” summarizes a set of acute, life-threatening stages of coronary artery disease, namely acute myocardial infarction with ST-segment elevations in the ECG (STEMI), acute myocardial infarction without ST-segment elevations in the ECG (NSTEMI) and unstable angina (UA). The latter two are also referred to as Non-ST-elevation acute coronary syndrome (NSTEMI). Cardinal symptom of ACS is acute chest-pain which, together with the patient’s medical history and nature of physical findings leads to the first diagnosis of “suspected acute coronary syndrome” with admission to Emergency Departments (EDs) and Chest Pain Units (CPUs). Despite the general knowledge that patients with ACS present themselves to the ED with chest pain, epidemiological data reveals that only about 50% of patients with chest pain do suffer from ACS, the rest of these patients are diagnosed with other cardiac or extra-cardiac, e.g. gastro-oesophageal, musculoskeletal, pleura-pulmonal, mediastinal or psychogenic conditions [1]. Further evaluation and decision-making in these patients largely depends on their Troponin blood level as it identifies high risk patients. Myocardial infarction has recently been defined in an expert consensus paper by the ESC/ACCF/AHA/WHF task force for the redefinition of myocardial infarction [2]. The diagnosis is based on a rise or fall of cardiac biomarkers together with either symptoms of ischemia, ECG-changes or imaging evidence of new loss of viable myocardium. The preferred biomarker is Troponin I or T drawn on first assessment

and 6-9 hours later. Thus, patients with a positive Troponin at baseline belong to a well defined patient group which can be treated according to standard guidelines. Unfortunately, in a population of patients with suspected acute coronary syndrome less than a quarter of the patients is tested positive for Troponin at presentation to the Emergency Department. In a chest pain evaluation by Newby et al. 1005 patients without ST-segment elevation in 6 chest pain units were tested for various cardiac biomarkers. At baseline, 13.7% of patients were positive for Troponin I, after serial testing this number grew to 26% [3]. In a trial performed by our site we enrolled 429 patients with suspected acute coronary syndrome of which 23.8% were initially Troponin I positive, including patients with ST-segment elevation [1]. In both trials the majority of patients were Troponin negative. It is one of the big challenges in Emergency Medicine to decide on whether a Troponin negative chest pain patient should be admitted to hospital for urgent catheterization, admitted to hospital for further evaluation and possibly later cardiac catheterization or should be discharged home for further ambulatory evaluation and care.

Pope et al. assessed the incidence of missed diagnoses of acute cardiac ischemia in the Emergency Department by analysing data from 10.689 patients with chest pain suggestive of acute coronary syndrome. 2.1 % of patients with acute myocardial infarction and 2.3% of patients with unstable angina were mistakenly discharged from the ED [4]. Given the huge impact this may have on the patient's life this is an unacceptably high number. On the other hand, fear of this potentially fatal error means that a large number of patients are being classified as suspected acute coronary syndrome and are therefore admitted to hospital for serial biomarker testing, monitoring and initialisation of medical treatment despite the absence of an acute illness. These patients are put at an unnecessary risk of side effects from the antithrombotic and anticoagulant medication which they receive as standard care for the duration of their ACS evaluation.

A new cardiac biomarker that provides "rule-out" information in a sense that patients at low risk can be identified straight after admission to the Emergency Department and can safely be transferred to ambulant care is highly sought after.

4.2 Rationale

Copeptin, a 39 amino acid glycopeptide, is the C-terminal portion of Pro-Vasopressin. It is co-secreted from the posterior pituitary gland together with Vasopressin and mirrors the amount of Vasopressin in the circulation. Vasopressin is primarily known as Anti-Diuretic Hormone (ADH), which acts in the kidney to regulate the body's retention of water and in high concentration causes arterial vasoconstriction.

Vasopressin is, as a central hormone, also a crucial part of the hypothalamo-pituitary-adrenal axis, which responds to severe, life-threatening "stress inputs"; its levels reflect the body's individual stress level [5 6].

Vasopressin itself has a half-life of 5-10 minutes and is therefore difficult to measure in-vivo. Copeptin is secreted stoichiometrically with Vasopressin, it remains stable for days after blood withdrawal and can therefore easily be measured [7]. Copeptin has been studied as a diagnostic and prognostic marker since 2006. In acute myocardial infarction Copeptin levels have been shown to increase early after the onset of symptoms (0-4 hours) and start decreasing after 4-5 hours [8]. In acute myocardial infarction two trials have investigated the prognostic value of Copeptin. Khan et al. assessed the value of Copeptin and NT-proBNP for the prediction of death and heart failure after 60 days in 980 patients with acute myocardial

infarction. Both biomarkers predicted outcome independently with an area under the curve of 0.75 for Copeptin and 0.76 for NT-proBNP. Copeptin plus NT-proBNP assessment had the highest predictive value with an AUC of 0.84 [7]. In a similar trial Voors et al. found Copeptin to have an even stronger predictive value than NT-proBNP and BNP in a study on 224 patients assessed 3 days after their acute myocardial infarction [9].

The first trial assessing the diagnostic value of Copeptin in acute myocardial infarction was conducted by Reichlin et al. They enrolled 487 patients in the Emergency Department with symptoms suggestive of myocardial infarction to measure Copeptin at presentation. Of these 487 patients 17% had a final diagnosis of myocardial infarction (37% STEMI and 63% NSTEMI), 17% of unstable angina, 13% of cardiac symptoms due to other cardiac causes, 43% had a non-cardiac disease and in 11% the symptoms were of unknown origin. Copeptin levels in this study were significantly higher in patients with acute myocardial infarction than in patients with other diagnoses (median 20.8 pmol/L vs. 6.0 pmol/L, $p < 0.001$). Copeptin significantly increased the diagnostic accuracy of Troponin from an area under the receiver operating curve (AUC) of 0.86 for Troponin T alone to 0.97 in a dual marker approach of Troponin T plus Copeptin which demonstrates that due to their different pathomechanisms Troponin, a marker of cardiac injury and Copeptin, a marker of stress, both identify patients that the other does not or to a lesser extent.

Further analysis by Reichlin et al. revealed that Copeptin in conjunction with Troponin T was particularly useful as a rule-out marker in acute myocardial infarction (AMI). TnT below 0.01 µg/L plus Copeptin below 14 pmol/L ruled out AMI at presentation with a sensitivity of 98.8% and a specificity of 77.1% (negative predictive value 99.7%) [8].

The most recent publication on Copeptin in acute myocardial infarction by Keller et al. validated these data. They tested the early diagnostic value of Copeptin, in addition to Troponin, in 1293 patients of which 244 had a discharge diagnosis of acute myocardial infarction and 211 of unstable angina. In this trial the combined measurement of Troponin and Copeptin again improved the identification of patients with AMI and provided a negative predictive value of 94.8 % (Copeptin cut-off 13 pmol/l), emphasising the value for a safe-rule out of AMI [10].

Copeptin is an extremely promising new cardiac biomarker that has the potential to improve the process of identifying high and low risk patients with suspected acute coronary syndrome. It is an optimal complement to Troponin regarding both pathomechanism and timing of elevation. Both markers combined could accelerate further patient management by bypassing the time that is required for serial Troponin testing and further diagnostic evaluation.

5 Study objectives

This is a multicentre biomarker randomized controlled trial to quantify the benefit of integrating the new biomarker Copeptin into the process of managing patients with suspected non ST-elevation acute coronary syndrome (N-STEACS) with a negative baseline Troponin I test result in the Emergency Department and Chest Pain Unit.

Hypothesis:

Patients with suspected ACS with a negative baseline Troponin who test negative for Copeptin at admission are at low risk of ACS and can safely be discharged into ambulant

care. These patients will not experience a higher rate of MACE within 30 days after their admission than patients who are managed by standard practise of care.

Secondary hypotheses:

Patients with suspected ACS with a negative baseline Troponin T who test positive for Copeptin at admission are at risk for ACS and should be evaluated as by standard of care. The Integration of Copeptin into the CPU process will shorten the patient's length of Emergency Department/ CPU and hospital stay and will improve patient satisfaction

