5.1 Primary endpoint

Rate of MACE (all- cause death or survived sudden cardiac arrest, myocardial infarction, re-hospitalisation for acute coronary syndrome, acute unplanned PCI, coronary artery bypass grafting (CABG) and documented life-threatening arrhythmias (VF, VT, AV-block III)) within 30 days Copeptin vs. Control group

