7.1 General Patient Flow

Consecutive N-STEACS patients of the Chest Pain Unit with a negative Troponin T at admission will be invited to participate. Troponin T is tested as part of the standard management of patients with suspected acute coronary syndrome. Patients who give their written informed consent will be randomized into one of two study arms (experimental and standard management).

Experimental Arm: Further management dependent on Copeptin result

1. Patients of the above described characteristics who test **negative for Copeptin** at admission will be considered low-risk. In these patients we abstain from further ACS evaluation and instead discharge them into ambulant care. Before discharge patients will have a final visit to secure their well-being. The visit includes a physical examination, an ECG and an assessment for MACE and bleeding events.

Patients who show any signs and symptoms of an acute illness requiring in-hospital treatment will not be discharged (see withdrawal criteria 5.3). This decision is at the discretion of the attending physician.

To secure the patients safety they will be discharged into each co-operating network of resident cardiologists . Patients are to see a cardiologist within a maximum of 3 days after discharge (if discharge falls on a Friday), preferably on the next day after discharge. Further appointments will be at the discretion of the resident cardiologist (see 7.2).

2. Patients with the above described characteristics who test **positive for Copeptin** at admission will be managed as by standard practice i.e. patients will be evaluated as by standard of care abiding current guidelines for the management of patients with suspected ACS

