7.5 Standard process

Copeptin results will not be revealed to the treating physicians. Patients will be managed as by standard practice i.e. patients will be evaluated as by standard of care abiding current guidelines for the management of patients with suspected ACS.

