8.4 Enrolment and randomization

Patients will be assigned to their study group by randomization via sealed envelopes as soon as the written informed consent has been signed.

The Copeptin test result will not automatically be communicated to the Emergency Department but will need to be requested via telephone after the randomization. It will only be released for patients in the experimental group. To assure this, the randomization letter for patients in the experimental group will contain a code which will be noted down in the central laboratory before releasing the Copeptin value.

The code can be compared with the code in the patient's randomization letter to proof adherence to this process.

In patients who are randomized to the control group, the Copeptin result will only be documented at the laboratory and will not be available to the investigators during the recruitment period.

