14.2.2 Analysis of endpoint

Safety of discharging patients with negative Troponin and negative Copeptin at baseline We chose a primary safety endpoint to prove that discharge of these patients does not increase their mortality or their risk for cardiac events like survived sudden cardiac arrest, myocardial infarction, re-hospitalisation for acute coronary syndrome, acute unplanned PCI, coronary artery bypass grafting (CABG) and documented life-threatening arrhythmias (VF, VT, AV-block III). [name] et al. saw a 6 week MACE rate of 6.4% in 266 patients with a serial negative Troponin result, who were evaluated for an acute coronary syndrome and a 7.8% MACE rate in all patients who were sent home after judgment of the attending physician.

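### The main hypothesis concerns discharged copeptin-negative patients, but the primary comparison is whole arm against whole arm; that dilutes harm in those patients and cannot alone support the claim about them

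*Protocol*

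**What the plan says.** **Claim.** The synopsis and section 5 state the main hypothesis for troponin-negative patients "who test negative for Copeptin at admission are at low risk of ACS and can safely be discharged into ambulant" (outpatient) care. Section 5 adds: "These patients will not experience a higher rate of MACE within 30 days after their admission than patients who are managed by standard practise". Section 14.2.2 opens its account of the endpoint analysis with "Safety of discharging patients with negative Troponin and negative Copeptin at baseline".

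**Comparison.** Section 5.1 and the synopsis define the primary endpoint as the MACE rate "within 30 days Copeptin vs. Control group". Neither restricts it by copeptin result. The synopsis gives the sample size per randomised group, 446 each.

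**Management by copeptin status.** In the experimental arm, negative patients are discharged early. The synopsis says that those "who test positive for Copeptin at admission will be evaluated as by standard of care according to current guidelines", and section 7.1 repeats this. For the control arm, section 7.5 prescribes standard care for everyone and states that "Copeptin results will not be revealed to the treating physicians".

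**Copeptin in controls.** Section 8.3 and the table in 8.6 take copeptin from the routine blood drawn at screening. Section 8.4 adds: "In patients who are randomized to the control group, the Copeptin result will only be documented at the laboratory", with the value withheld from investigators while recruitment runs.

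**Other analyses.** Sections 5.2.1 to 5.2.4 list no analysis by copeptin status. The predefined subgroups in 5.2.5 are sex, GRACE score and age.

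**The concern.** The claim is about one stratum of the experimental arm, while the named test concerns the whole arm. Early discharge, the part of the strategy that could cause harm, is prescribed only for copeptin-negative patients. Copeptin-positive patients add events to both arms and, as prescribed, no difference between them. They shrink the observed difference and add noise, which makes a finding of no higher rate easier to reach.

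The comparator wording in section 5 is a second, smaller fault. Patients under standard practice are not limited to copeptin-negative ones. Taken at its word, the sentence sets a group selected for low risk against a mixed-risk group.

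What is at stake is the trial's central conclusion. A satisfactory whole-arm result could be reported as proof that discharging copeptin-negative patients is safe, although their own risk had risen materially.

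**Working it through.** **Inputs from the protocol.** 446 per arm, 1:1 allocation (synopsis); Fisher's exact test for the main outcome (14.2.1); reference MACE rates of 6.4% and 7.8% (14.2.2). The figure of 446 cannot be reproduced, because the power calculation is in an appendix that is not shown. It is taken as given, and nothing below depends on how it was derived.

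**Assumptions, not in the protocol.** Copeptin-negative share q = 65% or 70%; MACE under standard care 3% in negatives; 14.5% (q = 65%) or 16.3% (q = 70%) in positives, chosen so that the arm rate is about 7%, between the two reference rates. Tests are at two-sided 5% or one-sided 2.5%. The 5-point margin is illustrative.

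**Step 1: dilution.** Whole-arm difference = q × (difference in negatives) + (1 − q) × (difference in positives). With positives managed as prescribed, the second term is zero. An arm-level tolerance of 5 points then allows 5/q in negatives: 5/0.70 = 7.1 points, 5/0.65 = 7.7 points.

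**Step 2: double the risk in negatives, 3% to 6%.**
- q = 65%: control 0.65 × 3 + 0.35 × 14.5 = 7.0%; experimental 0.65 × 6 + 0.35 × 14.5 = 9.0%.
- q = 70%: control 0.70 × 3 + 0.30 × 16.3 = 7.0%; experimental 0.70 × 6 + 0.30 × 16.3 = 9.1%.

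A 3-point excess in discharged patients appears as about 2 points between arms.

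**Step 3: chance of detecting it (exact Fisher power, two-sided 5%).** Negatives per arm: 0.65 × 446 = 290; 0.70 × 446 = 312.

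| q | Whole arm, 446 per arm | Negatives only |
|---|---|---|
| 65% | 15.5% | 35% (290 per arm) |
| 70% | 17.5% | 37% (312 per arm) |

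The smaller set has about twice the power, because the effect is undiluted and the base rate is lower.

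**Step 4: chance of passing a 5-point non-inferiority test despite the doubling.** Probability = Φ((5 − true difference)/SE − 1.96), in percentage points, with SE the square root of [p_c(1 − p_c) + p_t(1 − p_t)]/n.
- q = 65%: whole arm, difference 1.95, SE 1.82, probability 39%; negatives, difference 3.0, SE 1.72, probability 21%.
- q = 70%: whole arm, difference 2.10, SE 1.82, probability 36%; negatives, difference 3.0, SE 1.66, probability 23%.

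**Step 5: is the matching contrast valid?** The copeptin sample predates randomisation (8.3, 8.4, 8.6), so copeptin status is a baseline variable. It is recorded in both arms. Copeptin-negative experimental against copeptin-negative control is therefore a randomised comparison, provided that patients are analysed in the arm to which they were allocated.

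**The case against.** **The whole-arm comparison is the right primary.** Section 5 opens with the aim of quantifying the benefit of adding copeptin to the care process, and the synopsis randomises to two forms of process management. Whole arm against whole arm tests exactly that. This stands. A reader might infer that the primary analysis is invalid; the protocol does not support that.

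**Copeptin-positive patients may not be treated alike.** Section 9 concedes that they might be seen as high-risk and receive more intensive treatment, and their result is known in one arm only. This also stands. Equal care is what is prescribed, not what is guaranteed, and a negatives-only test would miss such an effect, so the whole-arm comparison should be kept. If closer care lowered MACE in positives, it would also offset harm in negatives within the whole-arm difference.

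**No section plans to test negatives against all controls.** Correct. A reader might take the sentence in section 5 as a planned test, in which 6% in discharged patients would look no higher than 7% in all controls despite a doubled risk. Sections 5.1, 14.2.1 and 14.2.2 plan nothing of the kind. It is loose wording to be corrected.

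**Restricting to negatives does not remove the risk of a false pass.** A doubling still passes a 5-point test about one time in five (step 4). The margin matters as well as the population, and the margin is not visible.

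**A supporting analysis may sit in the analysis plan.** Possibly, so its absence from 5.2.5 is weak evidence by itself. The mismatch between the hypothesis and the primary comparison, however, is fixed in the protocol.

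**Conclusion.** The point holds as a mismatch between claim and comparison. The whole-arm result answers whether the copeptin strategy raises MACE overall. On its own it cannot show that discharged copeptin-negative patients are no worse off. The direction follows from the protocol's text for any copeptin-negative share below 100%, as long as positives are managed as prescribed.

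The size rests on assumed values. At 65–70% negative, 3% MACE in negatives and about 7% per arm, a doubled risk in negatives is detected with 15–17% power for whole arms against 35–37% in negatives. It passes an assumed 5-point margin with probability 36–39% against 21–23%. Other shares, rates or margins change these figures.

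The documents do not show that the sample size is wrong or that the primary comparison should be replaced. This should be fixed, but it does not invalidate the design.

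**What to change.** 1. Keep the whole-arm comparison of 30-day MACE as primary, for the strategy.
2. Reword the hypothesis in section 5 so that the comparator is copeptin-negative patients managed by standard practice.
3. Prespecify, as a required supporting safety analysis, the 30-day MACE risk difference with confidence interval in copeptin-negative patients by the protocol's own 10 pmol/L cut-off, experimental against control. Analyse as randomised: section 10.1 excludes patients who cannot be discharged for other medical reasons, and such exclusions could fall unevenly between arms.
4. State that any claim about discharged patients will be made only with reference to that result.

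**Cost.** Protocol text and one further analysis; control copeptin values are already recorded and can be released after recruitment. The subset is smaller, so its interval is wider than if all 446 per arm were copeptin-negative.

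Making this analysis co-primary is not part of the fix, because it would need re-sizing. With 6.4% MACE in negatives, no true harm and a 5-point margin, 290–312 per arm gives only about 69–72% power. Keeping 446 negatives per arm at a 70% share would need 446/0.70 = 638 randomised per arm.
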